11. A clinically significant electrocardiogram (ECG) abnormality, including a marked baseline prolonged QT/correct QT interval (eg, a repeated demonstration of a corrected QT interval >460 ms)
12. Any history of clinically significant bradycardia or other clinically significant conduction abnormality
13. Any suicidal ideation with intent with or without a plan at Screening or within 6 months of Screening (ie, answering "Yes" to questions 4 or 5 on the Suicidal Ideation section of the Columbia-Suicide Severity Rating Scale [C-SSRS] or based on investigator's clinical judgment for subjects unable to be evaluated by C-SSRS)
14. Any lifetime suicidal behavior (per the Suicidal Behavior section of the C-SSRS or based on investigator's clinical judgment for subjects unable to be evaluated by C-SSRS)

15. Hypersensitivity to the study drug and any of the excipients
16. Scheduled for surgery during the study
17. Use of illegal recreational drugs
18. Currently enrolled in another clinical study or used any investigational drug or device within 4 weeks before Screening or within approximately 5 half-lives, whichever is longer.

Study Treatments

Test drug: E2023, oral, 10-mg tablets

Comparator Drug: placebo, oral tablets matching the test drug

Study drug will be taken as a suspension BID approximately 12 hours apart.

To prepare the suspension of study drug before each administration, 2 tablets (from a blister pack, assigned by interactive voice and web response system [IxRS]) will first be suspended in 10 mL of water, after which 70 mL of sugar-free Ora-Sweet Syrup will be added and the suspension mixed thoroughly. For subjects with weight <20 kg, a 20 mL aliquot of this suspension, or for subjects with weight \geq 20 kg, a 40 mL aliquot of this suspension will be taken orally and the remainder of the suspension should be discarded after each administration.

Duration of Treatment

14 weeks double-blind Treatment Period and 12 weeks open-label Extension Phase

Concomitant Drug/Therapy

Concomitant AEDs, including Epidiolex[®], initiated before Screening are allowed; the dose must remain stable during the Prerandomization and Randomization Phase.

Benzodiazepines are allowed as AEDs or rescue medication for seizure control.

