9.1.3 Extension Phase

The Extension Phase will consist of a Treatment Period (12 weeks) and a Follow-up Period (4 weeks). Subjects are eligible to complete the Extension Phase only if they have completed the Treatment Period of the Core Study.

All subjects will receive lorcaserin during the entire Extension Phase but the dose level will be blinded during the first 6 weeks. During the first 6 weeks of the Extension Phase, subjects who received lorcaserin during the Core Study will receive the same dose of lorcaserin (the dose will remain flexible per weight category, based on clinical response and tolerability); subjects who received placebo during the Core Study will receive the target dose of lorcaserin per weight category. During the second 6 weeks of the Extension Phase, all subjects will receive lorcaserin at the maximum dose per weight category (the dose may be decreased due to tolerability reasons and increased again if tolerability improves). Addition, deletion, and dose changes to concomitant AEDs are not allowed during the Treatment Period of the Extension Phase.

The Follow-up Visit will be conducted 4 weeks after the last dose of study drug for subjects who will not participate in the Extended Access Program (Study E2023-A001-405) after completion of this study. Subjects who complete the Extension Phase will be eligible to enter into Study E2023-A001-405. See [Appendix 2](#) for a full description of the Extension Phase.

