Statistical analyses will be performed by the sponsor or designee after the study is completed, the database is locked and released, and a snapshot of the database is obtained and released. Analyses for regional submissions may be performed during the course of the study. Statistical analyses will be performed using SAS software or other validated statistical software, as required. Details of the statistical analyses will be included in a separate statistical analysis plan.

Statistical and Analytical Plans

The statistical analyses of Extension Phase data are described in this section. Further details of the analytical plan will be provided in the statistical analysis plan, which will be finalized before database lock and treatment unblinding.

Study Endpoints

- Safety and tolerability, including incidence of treatment-emergent adverse events
- PK parameters of lorcaserin in the Treatment Period
- Percent change in frequency of convulsive seizures
- Percent change in frequency of each type of seizure
- Proportion of subjects who are free from convulsive seizures
- Proportion of subjects who are seizure-free
- Percent change from baseline in frequency of clusters
- Clinical Global Impression of Change
- Change from baseline in QOLIE-31 and PedsQL 4.0 Scales

Analysis sets

Safety Analysis Set is the group of subjects who received at least 1 dose of study drug and had at least 1 postdose safety assessment in the Extension Phase.

Full Analysis Set is the group of subjects who received at least 1 dose of study drug and had at least 1 postdose seizure measurement in the Extension Phase.

Efficacy Analyses

Descriptive statistics will be provided for the efficacy endpoints in the Extension Phase. Mean, standard deviation, median, minimum, and maximum will be provided for continuous endpoints and number and percentage will provide for categorical variables. In addition, plots will be used to summarize the data.

Safety Analyses

All safety analyses will be performed on the Safety Analysis Set. Safety data that will be evaluated include monitoring and recording all adverse events; regular laboratory evaluation for hematology, blood chemistry, and urinalysis; periodic measurement of vital signs, weight and ECGs; and the performance of physical and neurological examinations. Safety analyses will be performed similarly to the Core Study analyses and all analyses will be on the treatment duration (Core Study and Extension Phase).

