5.2 Study Subjects

5.2.1 Definitions of Analysis Sets

The Safety Analysis Set is the group of subjects who received at least 1 dose of study drug and had at least 1 postdose safety assessment.

The Full Analysis Set is the group of randomized subjects who received at least 1 dose of

Eisai Final 4.0 Confidential Page 11 of 30 study drug and had at least 1 postdose primary efficacy measurement.

The PK Analysis Set is the group of all randomized subjects from whom at least measurable lorcaserin plasma concentration was obtained with associated documented dosing history.

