5.9 Extension Phase Analyses

Efficacy Analyses

Descriptive statistics will be provided for the efficacy endpoints in the Extension Phase. Mean, standard deviation, median, minimum, and maximum will be provided for continuous endpoints and number and percentage will provide for categorical variables. In addition, plots will be used to summarize the data. Efficacy analyses will be performed similarly to the Core Study analyses and all analyses will be on the treatment duration (Core Study and Extension Phase).

Safety Analyses

All safety analyses will be performed on the Safety Analysis Set. Safety data that will be evaluated include monitoring and recording all adverse events; regular laboratory evaluation for hematology, blood chemistry, and urinalysis; periodic measurement of vital signs, weight and ECGs; and the performance of physical and neurological examinations. Safety analyses will be performed similarly to the Core Study analyses and all analyses will be on the treatment duration (Core Study and Extension Phase).

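### The combined Core-plus-Extension safety summary has two different denominators, and the protocol's version leaves out Core discontinuations due to adverse events

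*Protocol*

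**What the plan says.** Protocol Appendix 2 (Analysis sets) gives the Extension Phase its own Safety Analysis Set: dosed subjects who "had at least 1 postdose safety assessment in the Extension Phase". Section 9.1.3 sets the entry condition: "Subjects are eligible to complete the Extension Phase only if they have completed the Treatment Period of the Core Study". Under Safety Analyses, Appendix 2 then states that "all analyses will be on the treatment duration (Core Study and Extension Phase"). The synopsis gives the two durations as "14 weeks double-blind Treatment Period and 12 weeks open-label Extension Phase", 26 weeks in all.

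SAP 5.9 repeats the combined span and says "All safety analyses will be performed on the Safety Analysis Set". The SAP defines that set once, in 5.2.1, as subjects who "received at least 1 dose of study drug and had at least 1 postdose safety assessment". It gives no separate set for the Extension.

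Under Appendix 2, Core placebo subjects first receive lorcaserin in the Extension. The first Extension objective listed there is the safety and tolerability of lorcaserin.

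**The concern.** The protocol's set is chosen by an event at or after week 14, yet the analysis looks back over weeks 0 to 14. For anyone in the set, the Core weeks are time already known to have been completed. A subject who left in the Core because of an adverse event adds nothing to the numerator or the denominator of the combined summary. The measure hit most directly is TEAEs leading to discontinuation, which protocol 9.7.1.8 and SAP 5.6 both list as a planned summary.

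The SAP's set removes that selection but raises another question. It includes placebo subjects who left in the Core and never took lorcaserin. For placebo subjects who did cross over, the combined span joins 14 weeks on placebo to 12 weeks on lorcaserin. A pooled figure over that set is not a lorcaserin incidence.

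The longest safety summary in the trial could therefore be produced on either of two denominators, depending on which document the programmer follows.

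**Working it through.** **What can be reproduced.** The documents state no adverse-event rate, so there is no planned figure for this quantity to check. The only stated input on how many subjects might leave is the dropout allowance. SAP section 4: 54 / (1 - 0.12) = 61.4, rounded up to 62, as stated. Protocol 9.7.2 uses 7%: 54 / 0.93 = 58.06, against 58 stated. Both are all-cause allowances for both arms together, so they limit the plausible size of the excluded group but do not measure adverse-event stopping.

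**Step 1: the two rules side by side.**

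| | Protocol Appendix 2 | SAP 5.9 with 5.2.1 |
|---|---|---|
| Time span | Core + Extension | Core + Extension |
| Lorcaserin subject who left in the Core | excluded | included |
| Placebo subject who left in the Core | excluded | included, never took lorcaserin |
| Placebo subject who crossed over | included: 14 placebo + 12 lorcaserin weeks | same |

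**Step 2: TEAEs leading to discontinuation, lorcaserin-randomised arm.** Let c be the proportion stopping for adverse events in the Core and e the proportion of entrants stopping for them in the Extension. Assume that no one leaves the Core for other reasons and that all completers enter.

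- All exposed: 1 - (1 - c)(1 - e). Protocol's set: e.
- c = 5%, e = 3%: 1 - 0.95 × 0.97 = 7.9%, against 3%.
- c = 20%, e = 10%: 1 - 0.80 × 0.90 = 28%, against 10%.

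Both ranges are assumptions. In whole subjects, suppose 31 on lorcaserin, 4 leaving in the Core (3 for adverse events) and 1 more stopping for an adverse event in the Extension. The protocol's set gives 1/27 = 3.7%; all exposed gives 4/31 = 12.9%.

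**Step 3: the same with placebo crossovers pooled.** Take 31 per arm and assume the same Core loss on placebo. Lorcaserin-treated subjects number 31 + 31(1 - c), and discontinuations 31c + 2 × 31(1 - c)e.

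- c = 5%, e = 3%: (1.55 + 1.77) / 60.45 = 5.5%.
- c = 20%, e = 10%: (6.20 + 4.96) / 55.8 = 20%.

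The gap narrows from 8-28% to about 5.5-20%, against the same 3-10% among entrants.

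**Step 4: any adverse event.** Let d be the excluded share, p the incidence among included subjects and q among excluded subjects. The bias of the protocol's set is d(p - q). The table gives it in percentage points; d = 14.3% is 5/35, from the chart review in protocol 7.2 (five stopped before 30 days for side effects; the 35 analysed are assumed as denominator). The values of p and q are assumed.

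| d | q | p = 30% | p = 50% | p = 70% |
|---|---|---|---|---|
| 7% | 100% | -4.9 | -3.5 | -2.1 |
| 12% | 100% | -8.4 | -6.0 | -3.6 |
| 14.3% | 100% | -10.0 | -7.1 | -4.3 |
| 12% | 20% | +1.2 | +3.6 | +6.0 |

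If q = p the bias is zero. The sign depends on why subjects left and how long they had been exposed.

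**The case against.** The strongest reply is that the SAP already avoids the exclusion. Appendix 2 defers detail to the SAP, and SAP version 4.0 has one set with no Extension condition, so read literally it keeps Core stoppers. SAP 5.9 also says "Safety analyses will be performed similarly to the Core Study analyses and all analyses will be on the treatment duration (Core Study and Extension Phase"), and the Core analyses are by treatment group. If the Extension tables follow randomised group, placebo subjects who never took lorcaserin sit in the placebo column and do not dilute the lorcaserin rate. This stands as a possible reading. It does not settle the matter: the SAP neither says that it replaces the Appendix 2 set nor states the grouping for the combined period, and placebo and lorcaserin time are still mixed for crossovers.

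Second, no safety data are lost. The Core tables use all dosed subjects, and listings cover all adverse events, serious events and events leading to discontinuation. The Extension analyses are descriptive. With 22 randomised, individual stoppers are easy to find in a listing. All of this stands and limits the severity. At that size, though, one omitted stopper is 1/11 = 9% of an arm, assuming about 11 per arm.

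Third, a reader might infer that 26-week adverse-event incidence as a whole is biased low. The documents do not support that: only the discontinuation measure has a certain direction. A reader might also take the SAP's 12% as adverse-event stopping on lorcaserin and, with an assumed 5% in the Extension, compute 1 - 0.88 × 0.95 = 16.4%. That 12% is an all-cause sample-size allowance, so the figure has no basis in the plan.

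Finally, it is slightly too strong to say that every Core stopper is excluded. Subjects off drug may continue scheduled visits (protocol 9.3.3), and the last Core treatment visit also counts as the first Extension visit.

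**Conclusion.** The inconsistency is real: one time span, two denominators. Apart from the off-drug edge case above, the protocol's set omits Core TEAEs leading to discontinuation by construction, so that rate is biased low whenever any occur. For other adverse events a low bias is plausible, given the early side-effect stopping in the cited chart review, but it could be nil or reversed. The SAP's set keeps Core stoppers, but pooled across arms it does not describe lorcaserin exposure.

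The sizes in steps 2 to 4 are illustrative, since every adverse-event rate in them is assumed. This should be fixed before the tables are produced, but it does not threaten the trial's other conclusions. The termination changes in SAP section 7 do not withdraw or redefine the Extension safety tables, so the point remains open.

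**What to change.** In SAP 5.9 and protocol Appendix 2, name one set for the combined period: all subjects with at least one lorcaserin dose in either phase, including those who stopped in the Core. Count events and exposure from the first lorcaserin dose. Show results by original arm and overall, with n/N and exposure-adjusted rates. State the baseline for placebo crossovers, because SAP 8.2 places the safety baseline before randomisation for everyone. If tables of Extension entrants are kept, limit them to events with onset in the Extension.

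If Appendix 2 will not be amended again now that the trial is terminated, record the departure in SAP section 7. The cost is wording, one set flag and a derived date of first lorcaserin dose. No new data are needed.

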Version 4.0, 18 May 2024

Change	Rationale
Section 3.2 Added "The study is planned to be conducted in US, Canada, India, and China or Brazil (to be determined)." to describe the regions	The study will be expanded to new regions
Section 3 and Section 4 Updated the number of randomized subjects to achieve target number of subjects in the Full Analysis Set	To account for a higher drop-out rate assumption
Section 3.2 Added "centralized" to describe the randomization	Previously there was only one region, so we did not need to specify whether randomization was centralized or not as that was the only choice. In the current version, there are multiple regions. We added "centralized" to describe the type of randomization and to differentiate it from conducting randomization within each region. Centralized randomization is chosen because it controls the imbalance in treatment allocation in the overall population better compared to randomization within each region.
Section 5.2.4 Added region to demographic characteristics	Region added since the study will be expanded to new regions
Section 5.3 (Section 4.6.1 in the original version) Removed "4.6.1 Pooling of Centers This is a multicenter study to be conducted in the US and Canada. Decisions regarding pooling of data across sites that had low enrollment will be made and documented	Region, instead of site, will be included in analysis model
before treatment unblinding." Section 5.3.1 Deleted "a" before "covariates"	Typographical correction
Section 5.3.1 Added "Other covariates include region, baseline seizure frequency, and treatment-by-region interaction."	To account for new regions in analysis model
Section 5.3.3 Add "key secondary endpoint" for subgroup analysis	To perform sensitivity analysis for key secondary endpoint as well
Section 5.3.3 Replace "site" by "Region (US and Canada, India, and China/Brazil)"	Replace site by region since some sites may enroll one or two subjects
Section 5.3.3 Replace "Epilepsy syndrome" by "Seizure types"	To correct an inadvertent error.
Section 5.4.1 Updated efficacy analysis methodology to include region and treatment-by-region interaction as factors in the rank ANCOVA	To adjust for potential sources of heterogeneity in analysis model

Eisai Final 4.0 Confidential Page 1 of 30 May 18, 2024

Statistical 7 marysis 1 min	
Section 5.4.2 Updated key secondary efficacy analysis to adjust for region in Cochran-Mantel-Haenszel test	To adjust for potential sources of heterogeneity in Cochran-Mantel-Haenszel test
Section 5.8 Added region to exploratory analysis model and test	To adjust for potential sources of heterogeneity in analysis model and test
Section 7 Added "The sponsor has decided to terminate this study. With 22 subjects randomized, which represents for 35% of the planned number, only descriptive statistics for primary, secondary, and selected exploratory endpoints will be provided. Subgroup analysis will be limited to seizure type, while sensitivity analysis will not be conducted. Given the limited PK data, we will only provide summary statistics for plasma concentrations of lorcaserin. We will not derive steady-state PK parameters such as C _{max} and AUC, nor to explore relationships between exposure to lorcaserin and selected efficacy and safety endpoints."	To explain the changes in the planned analyses resulting from the study termination.
Section 9 Added region to SAS code step 2 and 3	To adjust for potential sources of heterogeneity in analysis model and imputation model
Updated the SAP signature page	Administrative change

Version 1.0, 26 Jun 2020

Change	Rationale
Section 2 Added additional fenfluramine stratification to the description of randomization, "The randomization will be stratified by previous treatment with fenfluramine (yes, no) and by weight categories (10 to <20 kg, 20 to <40 kg, and ≥40 kg)."	Subjects previously treated with fenfluramine strata needs be balance by randomization.
Added fenfluramine strata to Section 4.6.2 Adjustment of	Fenfluramine strata added since randomization
Covariates and Section 4.6.4 Examination of Subgroups	stratification was change.
Section 4.9.1; added fenfluramine strata to primary analysis model	Fenfluramine strata added since randomization stratification was change.
Section 4.13 added fenfluramine strata to exploratory analysis model	Fenfluramine strata added since randomization stratification was change.
Section 2 added "The stratification factors will be balance between treatment groups using restricted randomization method proposed by Pocock and Simon (1975)." in the 4 th paragraph	As per FDA suggestion
Section 4.6.1 Added "Canada"	In order to help with recruitment Canadian sites were added.
Section 4.91. The primary model was simplified. Two and three way interactions were removed. In addition, site was removed from the model due to some sites only contributing 1 to 2 subjects.	As suggested by FDA
Section 4.9.2 fenfluramine strata added to CMH test and site remove.	As suggested by FDA
Section 9: fenfluramine strata was added to multiple imputation models. Site was deleted from imputation models	Added fenfluramine strata as a randomization strata. Site is deleted since some sites may enroll one or two subjects. This may cause multiple simulations to not converge.

Eisai Final 4.0 Confidential Page 3 of 30

STATISTICAL ANALYSIS PLAN

Study Protocol Number:

E2023-A001-304

Study Protocol A Multicenter, Double-Blind, Randomized, Placebo-Controlled, Title:

Parallel-Group Study with Open-Label Extension Phase of Lorcaserin

as Adjunctive Treatment in Subjects with Dravet Syndrome

Date: 18 May 2024

Version: Final Version 4.0

Eisai Final 4.0 Confidential Page 4 of 30

2 LIST OF ABBREVIATIONS AND DEFINITIONS OF TERMS

Abbreviation	Term
ACMV	available cases missing value
AE	adverse event
ANCOVA	analysis of covariance
ATC	anatomical therapeutic class
BOCF	baseline observation carried forward
BMI	body mass index
CI	confidence interval
СМН	Cochran-Mantel-Haenszel
CRF	case report form
CSR	clinical study report
FAS	full analysis set
FCS	Fully Conditional Specification
LOCF	last observation carried forward
LS	least squares
MedDRA	Medical Dictionary for Regulatory Activities
MI	Multiple Imputation
MNAR	Missing not at Random
PD	pharmacodynamic
PK	pharmacokinetic
PMM	Predictive Mean Matching
SAE	serious adverse event
SAP	statistical analysis plan
SE	standard error
SI	Système International
TEAE	treatment-emergent adverse event
TLG	tables, listings, and graphs
US	United States
WHO	World Health Organization

Eisai Final 4.0 Confidential Page 7 of 30 May 18, 2024

3 INTRODUCTION

The purpose of this statistical analysis plan (SAP) is to describe the procedures and the statistical methods that will be used to analyze and report results for Eisai Protocol E2023-A001-304.

3.1 Study Objectives

3.1.1 Primary Objective

The primary objective of the study is to demonstrate that lorcaserin has superior efficacy compared to placebo on percent change in frequency of convulsive seizures per 28 days in subjects with Dravet syndrome.

3.1.2 Secondary Objectives

3.1.2.1 Key Secondary Objective

• The key secondary objective of the study is to evaluate whether lorcaserin has superior efficacy compared to placebo on the 50% responder rate (percent of subjects with at least 50% reduction in frequency of convulsive seizures per 28 days compared to baseline).

3.1.2.2 Other Secondary Objective

- To evaluate whether lorcaserin has superior efficacy compared to placebo on the proportion of subjects who are free from convulsive seizures
- To characterize the pharmacokinetics (PK) of lorcaserin and the relationship between lorcaserin plasma concentrations, efficacy, and safety
- To evaluate the safety and tolerability of lorcaserin in subjects with Dravet syndrome

